6.2. Trial procedures

During treatment on this protocol, all patients will be followed and monitored as follows:

Table 6. Trial Procedures.

		Cycle						Following	Following completion	al ¹¹
D 1	D	l,	1		2	4	0	each	of even	viv
Required	Pre-	Day		2	3	4	8	cycle thru	numbered	Sur
studies	therapy ¹²		week	weeks	weeks	weeks	weeks	12 cycles ¹	cycles	01
Clinic visit	X	X		X		X	X	X	X	
H&P	X	X^{10}		Х		X	X	Х	Х	
Vital signs and PS	Х	Х		Х		Х	Х	Х	Х	
PTT, PT, INR	Х									
CBC, Diff, platelets	Х	X ⁹		Х		Х	Х	Х	Х	
Comprehensive Panel, Mg ²	X ³	X ⁹		Х		Х	Х	Х	Х	
Urine dip ³	Х					Х	Х	Х	Х	
TSH, free T4 ⁴	Х	X ^{9,}		Х		Х			Х	
Clinical										
toxicity				Х		Х	Х	Х	Х	
assessment										
Radiologic										
imaging for	v						v		\mathbf{v}	
tumor	Λ						Λ		Λ	
measurement ⁵										
Pregnancy Test ⁶		X ⁹								
Informed	v									
Consent	Λ									
Planned dose				v	v					
escalation ⁷				Λ	Λ					
Telephone										
assessment of			Х		Х					
toxicities ⁸										
Survival										v
Monitoring										Λ

- 1- Following completion of 12 cycles, assessments will be obtained every 8 weeks.
- 2- Comprehensive Panel includes Basic Panel (Na, K, Cl, CO2, BUN, Cr, Gluc), AST/SGOT, ALT/SGPT, Alk Phos, T.bili, Alb, Ca, Total Protein. Also will obtain magnesium.
- 3- Urine dipstick may be done in clinic or lab.
- 4- Serum or plasma Thyroid Function Tests (Free T4 and TSH) should be performed within 14 days of starting treatment. Subsequently, TSH should be done every 2 weeks X 2, then following completion of even numbered cycles of chemotherapy.

- 5- Radiologic imaging of the areas involved with recurrent/metastatic disease, such as the neck, chest, or other areas if needed because of the location of the metastatic disease; baseline within 28 days prior to treatment. On study assessments, may be within +/- 2 weeks. Imaging will be interpreted by Choi Criteria, interpretation to be performed by centralized UMCC Tumor Response and Assessment Core (TRAC).
- 6- Pregnancy test (urine or serum) will be performed for women of childbearing age within 3 days before first dose of Axitinib and if clinical concern for pregnancy arises.
- 7- Dose escalation is planned at 2 weeks (to 7 mg BID) and 3 weeks (to 10 mg BID), in the absence of toxicities grade 2 or greater. Dose escalation may be resumed after 1 week if all toxicities have diminished to grade 1 or less (see below), and measures have been taken to reasonably prevent recurrence of these toxicities with the higher dose.

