- 8- Telephone call to the patient must be made by a study staff member (RN or MD with a current nursing/medical license) at 1 and 3 weeks. During these calls, toxicity assessment will be conducted, per patient report, and toxicity management advice given, including initiation or titration of anti-hypertensive treatment. During the Week 3 call, if toxicities are grade 1 or less dose escalation to 10 mg BID will be made.
- 9- All baseline labs are required within 14 days of starting treatment (Cycle 1, Day 1).
- 10-H&P not required on Cycle 1, Day 1 if performed for screening within 72 hours
- 11- Survival assessment can be done by phone and will be performed once every three months (+/- 1 month)
- 12-Labs are eligible for screening if obtained within the past 28 days

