6.3 Initial Clinical Evaluation

- 1. Complete history and physical exam.
- 2. CBC with differential and platelet count (CBCDP); within 14 days prior to start of treatment
- Serum chemistry profile to include: comprehensive panel (Na, K, Cl, CO2, BUN, Cr, Gluc, AST/SGOT, ALT/SGPT, Alk Phos, T.bili, Alb, Ca, Total Protein), serum magnesium; within 14 days prior to start of treatment.
- 4. Urine dip (in clinic or lab)
- 5. TSH, free T4; within 14 days prior to start of treatment
- 6. Pregnancy test (serum or urine Beta-HCG) in women of childbearing potential; within 3 days prior to start of treatment.
- 7. Radiologic imaging of the areas involved with recurrent/metastatic disease, such as the neck, chest, or other areas if needed because of the location of the metastatic disease; within 28 days prior to treatment.

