12.2. Reporting Period

Adverse events reporting, including suspected, unexpected serious adverse reactions, will be carried out in accordance with applicable local regulations. For serious adverse events, the reporting period to Pfizer, Inc. or its designated representative begins from the time that the subject has taken at least one dose of trial treatment through the last subject visit. Any serious adverse event occurring any time after the reporting period must be promptly reported if a causal relationship to Axitinib is suspected.

Adverse events should be recorded on the CRF from the time the subject has taken at least one dose of trial treatment through last subject visit.

If a patient begins a new anticancer therapy, the adverse event reporting period for non-serious adverse events ends at the time the new treatment is started. Death must be reported if it occurs

during the serious adverse event reporting period after the last dose of investigational product, irrespective of any intervening treatment.

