12.3. Definition of an Adverse Event

An adverse event is any untoward medical occurrence in a clinical investigation subject administered a product or medical device; the event need not necessarily have a causal relationship with the treatment or usage. Examples of adverse events include but are not limited to:

- Abnormal test findings;
- Clinically significant symptoms and signs;
- Changes in physical examination findings;
- Hypersensitivity.

Additionally, they may include the signs or symptoms resulting from exposure in Utero.

Worsening of signs and symptoms of the malignancy under trial should be reported as adverse events in the appropriate section of the CRF. Disease progression assessed by measurement of malignant lesions on radiographs or other methods should not be reported as adverse events.

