12.6. Hospitalization

Adverse events reported from clinical studies associated with hospitalization or prolongation of hospitalization are considered serious. Any initial admission (even if less than 24 hours) to a healthcare facility meets these criteria. Admission also includes transfer within the hospital to an acute/intensive care unit (e.g., from the psychiatric wing to a medical floor, medical floor to a coronary care unit, neurological floor to a tuberculosis unit).

Hospitalization does not include the following:

- Rehabilitation facilities;
- Hospice facilities;
- Respite care (e.g., caregiver relief);
- Skilled nursing facilities;
- Nursing homes;
- Routine emergency room admissions;
- Same day surgeries (as outpatient/same day/ambulatory procedures).

Hospitalization or prolongation of hospitalization in the absence of a precipitating, clinical adverse event is not in itself a serious adverse event. Examples include:

- Admission for treatment of a preexisting condition not associated with the development of a new adverse event or with a worsening of the preexisting condition (e.g., for work-up of persistent pre-treatment lab abnormality);

- Social admission (e.g., subject has no place to sleep);

- Administrative admission (e.g., for yearly physical exam);

- Protocol-specified admission during a clinical trial (e.g., for a procedure required by the trial protocol);

- Optional admission not associated with a precipitating clinical adverse event (e.g., for elective cosmetic surgery);

- Pre-planned treatments or surgical procedures should be noted in the baseline

documentation for the entire protocol and/or for the individual subject;

- Admission exclusively for the administration of blood products.

Diagnostic and therapeutic non-invasive and invasive procedures, such as surgery, should not be reported as adverse events. However, the medical condition for which the procedure was performed should be reported and it meets the definition of an adverse event. For example, an

acute appendicitis that begins during the adverse event reporting period should be reported as the adverse event, and the resulting appendectomy should be recorded as treatment of the adverse event.

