Overall and progression-free survival rates at 2, 4 and 6 months will be reported along with 95% confidence intervals based on the binomial distribution. Kaplan-Meier methods will also be conducted to estimate these rates and the medians of PFS and overall survival (OS) of the 37 evaluable patients, with a corresponding standard error estimate based on Greenwood's formula (53).

Among this cohort of patients, progression will be determined based on Choi critieria.

- To determine the response.

The best overall response rate will be determined for each evaluable patient at 8 and 16 weeks following the start of Axitinib. The proportion of evaluable patients who have an objective response (complete or partial) and stable disease will be calculated, and a 95% exact binomial confidence interval will be determined.

- To determine the toxicity profile of this treatment regimen.

The proportion of treated patients experiencing any clinically significant (Grade 3 or worse) toxicity will be determined, with a 95% exact binomial confidence interval; specific toxicities of all grades will be tabulated.

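### No graded symptom baseline is scheduled before the first dose, so pre-existing symptoms, mainly from prior treatment, may be counted as on-treatment toxicity

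*Combined protocol and SAP*

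**What the plan says.** **Collection.** Section 12.2 states: "Adverse events should be recorded on the CRF from the time the subject has taken at least one dose of trial treatment", and collection runs to the last subject visit. Table 6 (section 6.2) is introduced with the words "During treatment on this protocol, all patients will be followed and monitored as follows". Its clinical toxicity row is marked at weeks 2, 4 and 8 and after later cycles, with nothing under Pre-therapy or Day 1. Telephone contacts at weeks 1 and 3 add to this: "During these calls, toxicity assessment will be conducted, per patient report". Section 7.1 likewise places toxicity assessment at the follow-up visits and in these calls.

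**Baseline.** Section 6.3 begins with "Complete history and physical exam" and goes on to laboratory tests and imaging. Table 6 adds vital signs and performance status. Neither asks for a CTCAE grade of symptoms already present.

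**Definition and grading.** Section 12.3 says of the cancer itself: "Worsening of signs and symptoms of the malignancy under trial should be reported as adverse events". Its general list of examples includes clinically significant signs and symptoms, with no condition that they be new. Section 12.7 has the investigator grade the event at its worst intensity under CTCAE v4.03.

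**Analysis.** Section 13.4 gives the proportion of treated patients with any Grade 3 or worse toxicity, with an exact 95% interval, and adds that "specific toxicities of all grades will be tabulated". Section 14.2 tabulates incidence, maximum severity and relationship to axitinib. Neither mentions a baseline grade.

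**The concern.** In a single-arm trial there is no control group to show how often a symptom would be reported without the drug. The patient's own state before treatment is the only reference within the trial, and for symptoms the plan schedules no graded record of it.

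The population makes this a practical matter. Section 5.2 admits patients with performance status up to 2. Section 5.3 excludes radiotherapy only within 2 weeks and major surgery only within 4 weeks of starting. No eligibility criterion requires effects of earlier treatment to have resolved. Background Table 2 lists, among frequent events on axitinib, fatigue (55.1%), dysphonia (34.0%), weight loss (25.6%) and stomatitis (15.7%). A pretreated head and neck cancer patient could plausibly bring any of these into the trial.

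What is at stake is secondary objective 5 in section 3.2, the toxicity profile. If long-standing symptoms enter the tables, the profile shows axitinib as less well tolerated than it is. Analysts could not reliably correct this later, because a grade that was never recorded has to be guessed from clinical notes.

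**Working it through.** The plan states no figure on this point, so there is nothing to recompute. The check is whether anything between screening and the final tables separates a pre-existing symptom from a new one.

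1. **Is a grade taken before the first dose?** Not by the protocol. The Table 6 toxicity row is blank at Pre-therapy and Day 1, both telephone calls follow the first dose, and 6.3 asks for history and examination without grading.
2. **Does the adverse event definition exclude unchanged symptoms?** In part. For signs and symptoms of the malignancy, 12.3 names worsening as what is to be reported, which weighs against recording stable ones. It is silent on residual effects of surgery, radiotherapy or chemotherapy.
3. **Does another section supply the rule?** Section 12.6 draws the distinction for one purpose. An admission does not in itself make a serious adverse event if it is "Admission for treatment of a preexisting condition not associated with the development of a new adverse event" or with worsening of that condition. This governs how admissions are classified, not what enters the toxicity tables.
4. **Does the recorded grade carry the change?** No. Section 12.7 asks for maximum intensity, not change from a starting grade.
5. **Does the analysis apply a rule?** No. Neither 13.4 nor 14.2 limits its counts to new or worsened events. The words treatment-emergent appear only in the title of Table 2, which summarises earlier axitinib data. The Grade 3 or worse proportion in 13.4 is not restricted by relationship to axitinib either.

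Take as an example a patient with stable Grade 2 dysphonia since earlier radiotherapy. The screening history may note hoarseness but gives no grade. Under 12.11 the patient is questioned about adverse events, and the symptom is present at the week 1 call and the week 2 visit. One member of staff may leave it out as long-standing. Another may record it as a clinically significant symptom, Grade 2, not related. The text permits both. In the second case it enters the all-grade table in 13.4 and the maximum-severity table in 14.2; only the relationship table sets it apart.

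Laboratory events differ. Blood counts, chemistry, thyroid tests and a urine dipstick are taken before treatment, so their baseline grades can be derived.

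The primary endpoint in 13.1 is being alive 6 months after the start of treatment. No toxicity grade enters that endpoint, its test or the sample size.

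**The case against.** The strongest reply is that starting adverse event recording at the first dose merely sets an on-treatment window, and that nothing tells staff to enter conditions that began earlier. Section 12.3 speaks of worsening for cancer symptoms. Pre-existing problems will be in the history and examination, causality must be assessed for every event, and 14.2 plans tables by relationship. The CRF pages are not among the documents and may include a baseline symptom page. Most of this stands, and it limits the point to a rule left open. It does not settle how residual treatment effects are handled, give worsening a recorded starting grade, or add a baseline reference to 13.4.

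Four stronger readings are tempting, and the documents do not support them:

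- **Pre-existing symptoms will be tabulated as toxicity.** The text leaves this open, and for symptoms of the cancer it leans the other way.
- **The inflation can be put in percentage points.** No baseline prevalence or carry-over rate is given, so any figure would rest wholly on assumption.
- **The relationship tables are defeated because 12.8 handles unknown cause as related.** That rule is stated for reporting purposes as defined by the company supplying the drug. Nothing extends it to the tables in 14.2.
- **An ungraded baseline symptom creates a contradiction in the dose-escalation condition**, "in the absence of toxicities grade 2 or greater". The wording is silent on pre-existing symptoms, and no two sections conflict on that question.

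**Conclusion.** The gap is real but modest. The protocol schedules no graded symptom assessment before the first dose and has no new-or-worsened rule for its toxicity tables. Some pre-existing symptoms, mainly residual effects of prior treatment, may therefore be counted as on-treatment toxicity. The direction, if it happens, is upward in the all-grade and maximum-severity tables, and possibly in the Grade 3 or worse proportion. The size cannot be determined from the documents.

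The conclusion assumes that the CRF has no baseline symptom page which the protocol fails to mention, and that some patients enter with persisting symptoms, which eligibility allows. It affects one secondary objective. The primary endpoint, its test and the power are untouched. This is a cheap improvement, not a flaw that threatens the trial's main conclusion.

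**What to change.** - **Table 6:** mark the clinical toxicity assessment in the Pre-therapy or Cycle 1 Day 1 column, to be done before the first dose.
- **CRF:** record each symptom then present with its CTCAE v4.03 grade.
- **Sections 13.4 and 14.2:** state that the toxicity tables and the Grade 3 or worse proportion count events that are new after the first dose or of higher grade than at baseline. For laboratory events, take the baseline grade from the pre-treatment values already collected.

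The cost is a few minutes at a visit that already includes history and examination, one extra CRF page, and a sentence in each of the two analysis sections. No extra visit or test is needed.

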12.3. Definition of an Adverse Event

An adverse event is any untoward medical occurrence in a clinical investigation subject administered a product or medical device; the event need not necessarily have a causal relationship with the treatment or usage. Examples of adverse events include but are not limited to:

- Abnormal test findings;
- Clinically significant symptoms and signs;
- Changes in physical examination findings;
- Hypersensitivity.

Additionally, they may include the signs or symptoms resulting from exposure in Utero.

Worsening of signs and symptoms of the malignancy under trial should be reported as adverse events in the appropriate section of the CRF. Disease progression assessed by measurement of malignant lesions on radiographs or other methods should not be reported as adverse events.

12.4. Abnormal Test Findings

The criteria for determining whether an abnormal objective test finding should be reported as an adverse event are as follows:

- Test result is associated with accompanying symptoms; and/or

- Test result requires additional diagnostic testing or medical/surgical intervention; and/or
- Test result leads to a change in trial dosing outside of protocol-stipulated dose

adjustments or discontinuation from the trial, significant additional concomitant drug treatment, or other therapy; and/or

- Test result is considered to be an adverse event by the investigator

Merely repeating an abnormal test, in the absence of any of the above conditions, does not constitute an adverse event. Any abnormal test result that is determined to be an error does not require reporting as an adverse event.

12.5. Serious Adverse Events

A serious adverse event or serious adverse drug reaction is any untoward medical occurrence at any dose that:

- Results in death;
- Is life-threatening (immediate risk of death);
- Requires inpatient hospitalization or prolongation of existing hospitalization;
- Results in persistent or significant disability/incapacity;
- Results in congenital anomaly/birth defect.

Progression of the malignancy under study (including signs and symptoms of progression) should not be reported as serious adverse events unless the outcome is fatal during the trial or within the safety reporting period. Hospitalizations due to signs and symptoms of disease

progression should not be reported as serious adverse events. If the malignancy has a fatal outcome during the study or within the safety reporting period, then the event leading to death must be recorded as an adverse event and as a serious adverse event with CTC grade 5 (See Severity Assessment). Medical and scientific judgment should be exercised in determining whether an event is an important medical event. An important medical event may not be immediately life-threatening and/or result in death or hospitalization. However, if it is determined that the event may jeopardize the subject and may require intervention to prevent one of the other outcomes, the important medical event should be reported as serious. Examples of such events are intensive treatment in an emergency room or at home for allergic bronchospasm; blood dyscrasias or convulsions that do not result in hospitalization; or development of drug dependency or drug abuse.

12.6. Hospitalization

Adverse events reported from clinical studies associated with hospitalization or prolongation of hospitalization are considered serious. Any initial admission (even if less than 24 hours) to a healthcare facility meets these criteria. Admission also includes transfer within the hospital to an acute/intensive care unit (e.g., from the psychiatric wing to a medical floor, medical floor to a coronary care unit, neurological floor to a tuberculosis unit).

Hospitalization does not include the following:

- Rehabilitation facilities;
- Hospice facilities;
- Respite care (e.g., caregiver relief);
- Skilled nursing facilities;
- Nursing homes;
- Routine emergency room admissions;
- Same day surgeries (as outpatient/same day/ambulatory procedures).

Hospitalization or prolongation of hospitalization in the absence of a precipitating, clinical adverse event is not in itself a serious adverse event. Examples include:

- Admission for treatment of a preexisting condition not associated with the development of a new adverse event or with a worsening of the preexisting condition (e.g., for work-up of persistent pre-treatment lab abnormality);

- Social admission (e.g., subject has no place to sleep);

- Administrative admission (e.g., for yearly physical exam);

- Protocol-specified admission during a clinical trial (e.g., for a procedure required by the trial protocol);

- Optional admission not associated with a precipitating clinical adverse event (e.g., for elective cosmetic surgery);

- Pre-planned treatments or surgical procedures should be noted in the baseline

documentation for the entire protocol and/or for the individual subject;

- Admission exclusively for the administration of blood products.

Diagnostic and therapeutic non-invasive and invasive procedures, such as surgery, should not be reported as adverse events. However, the medical condition for which the procedure was performed should be reported and it meets the definition of an adverse event. For example, an

acute appendicitis that begins during the adverse event reporting period should be reported as the adverse event, and the resulting appendectomy should be recorded as treatment of the adverse event.

12.7. Severity Assessment

If required on the adverse event case report forms, the investigator will use the following definitions of severity in accordance with National Cancer Institute Common Terminology Criteria for Adverse Events (CTCAE) Version 4.03 to describe the maximum intensity of the adverse event. If the event is serious, the CTCAE grade reported in the adverse event CRF must be consistent with the description of CTCAE grade included in the narrative section of the serious adverse event report.

GRADE	Clinical Description of Severity
0	no change from normal or reference range
1	mild adverse event
2	moderate adverse event
3	severe adverse event
4	life-threatening or disabling adverse event
5	death related to adverse event

Note the distinction between the severity and the seriousness of an adverse event. A severe event is not necessarily a serious event. For example, a headache may be severe (interferes significantly with subject's usual function) but would not be classified as serious unless it met one of the criteria for serious adverse events, listed above.

